
Date: _____

HOVER PROTOCOL SUMMARY

Title:	The HOVER Study: Heterotopic Implantation Of the Sapien 3 Transcatheter Aortic Valve in the Inferior Vena cava for the treatment of severe tricuspid Regurgitation
Design:	This is a prospective multi-center, non-blinded (open label), non-randomized safety and feasibility study of the heterotopic implantation of the Sapien 3 valve in the inferior vena cava for the treatment of severe tricuspid regurgitation in patients who are inoperable or at a very high surgical risk for tricuspid valve replacement. A total of 15 patients will undergo implantation. Primary endpoints will be assessed at 30-days and 6-months. This study is an off-label use of an FDA-approved and commercially available medical device.
Study Objectives:	#1: Determine the short term safety (<30 days) of Caval Valve Implant (CAVI) #2: Determine the intermediate term (6 months) efficacy of CAVI on palliation of patient symptoms of right heart congestion.
Primary Endpoints:	#1: Safety as defined by successful vascular access without unplanned major vascular complication as defined by VARC-2, delivery and retrieval of the transcatheter valve delivery system, correct position of both the vascular stent(s) and transcatheter valve in the IVC, a single valve placed within the IVC, and no need for additional surgery or re-intervention (including drainage of pericardial effusion) with the patient being alive at 30-days. #2: Efficacy as defined by Improvement of KCCQ score >15, or improvement in 6-minute walk test (6MWT)>70 meters or improvement of greater than 6% of peak Vo2 in cardiopulmonary exercise testing.
Population:	Patients with severe symptoms (NYHA class III-IV) and signs of peripheral and venous congestion (specifically lower extremity edema and abdominal ascites requiring diuretics), resulting from documented severe tricuspid regurgitation. These patients may benefit from tricuspid valve repair or replacement, but are believed to be at high risk or are deemed inoperable for standard tricuspid valve surgery as assessed by at least one cardiac surgeon.
Phase:	1-2
Clinical Sites:	
 1. Henry Ford Hospital, Detroit, Michigan – site PI: [name] [name] (Coordinating Center) 2. Temple University Hospital, Philadelphia, Pennsylvania – site PI: [name], DO 3. University of California San Francisco, San Francisco, California – site PI: [name] 4. Baptist Hospital of Miami, Miami, FL – site PI: [name]

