2.3 Statistical Analysis

A total of up to 15 patients will be enrolled. Due to the lack of preliminary data as well as exploratory nature of the study, no sample size and power analyses were performed. We expect to screen approximately 45 patients to enroll up to 15 eligible patients into this trial.

All clinically relevant baseline and follow-up data will be tabulated. Means (SDs), medians (ranges), and 95% confidence intervals will be reported for continuous variables and frequencies, percentages, and 95% confidence intervals for categorical variables. Specifically, each of the two primary endpoints (the procedural success at 30-days and the composite binary response variable at 6-months) will be summarized using both a point estimate and its exact confidence interval based on a binomial distribution. Other binary safety and efficacy secondary endpoints will be analyzed similarly. Continuous secondary endpoints (e.g., hemodynamics data) will be reported using descriptive summary statistics as well as a point estimate and its confidence interval based on a normal distribution assumption. The changes from baseline to each follow-up timepoint will additionally be evaluated using the McNemar matched pairs test for dichotomous variables and the t-test for continuous variables. In the presence of distributional non-normality, the Wilcoxon signed rank test will be used instead of the t-test. Data transformations such as log or square-root may also be considered. The analyses of NYHA functional classification will involve comparison of the baseline and post-operative (at each timepoint) functional class and determination of the percentages of patients improving, not changing, or worsening at each postoperative timepoint. The same principle will be applied to quality of life score (KCCQ) and 6-minute walk distance. Although this is an exploratory analysis, we anticipate 50% of patients will demonstrate improvement in one of the three pre-specified components of the primary efficacy outcome.

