During the entire study period, adverse events will be closely monitored by the trial PI and clinical trial coordinator of this study, working along with the study DSMB. In particular, formal stopping rules on the 6-month mortality are stipulated in this protocol (please refer to section 4.1 “Efforts to minimize procedure risks”). In addition, in the event that other adverse events (e.g., surgical complications) are thought to be excessive for the study patient population at any point of the trial, the patient accrual to the trial will be suspended immediately, pending a review of all adverse events data. A final decision will be made by the trial PI and DSMB as to whether the trial should be amended, terminated or continue accrual. Such decision should be filed with and pre-approved by the institutional IRB.

2.4 Study Endpoints:

The primary safety endpoint is procedural success at 30-days. Procedural success will include:

- Successful vascular access without unplanned major vascular complication as defined by VARC-2, delivery and retrieval of the transcatheter valve delivery system, correct position of both the vascular stent(s) and transcatheter valve in the IVC, a single valve placed within the IVC, and no need for additional surgery or re-intervention (including drainage of pericardial effusion) with the patient being alive at 30-days.

The primary efficacy endpoint will be improvement in one of three variables assessed from baseline to 6-months.

- Improvement of KCCQ score >15. This has been shown to correlate with improvement in quality of life with heart failure patients²².
- Improvement in 6-minute walk test (6MWT)>70 meters. This has been shown to provide prognostic information in patients with congestive heart failure after an intervention²³.
- Improvement of greater than 6% of peak Vo2 in cardiopulmonary exercise testing. In a heart failure population, this has been shown to help assess prognosis in patients who were instituted in an exercise program ²⁴.

Secondary endpoints will be evaluated at several timepoints and will be divided into safety and efficacy: The first in the acute setting which will be out to 30 days or hospital discharge whichever being longer; additional time points will be at midterm (6 months post-procedure), long term (1 year and annually up to 5-years post-procedurally.)

Secondary safety endpoints include:

- All stroke and TIA (VARC-2)
- Mortality (VARC-2)
- Myocardial infarction (VARC-2)

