4.1.2. Data Safety Monitoring Board (DSMB)

A DMSB will be established. The DSMB is independent from the Sponsor, the investigators, or anyone involved in the medical care of the study subjects. Members will not have scientific, financial, or other conflict of interest related to the Sponsor or the investigators. The committee will be selected by the overall Principal Investigator and managed independently.

The members must have the following characteristics:

- working professionally as physicians or statisticians;
- at least one member with specific expertise in cardiothoracic surgery clinical trials;
- no relevant conflicts of interest;
- they will not be involved in the conduct of this trial in any other capacity, such as principal investigators, sub-principal investigators;
- they will not be engaged in any simultaneously occurring competitive trials;
- they should not be on the NIDPOE or debarred list of investigators.

Members will not serve on the DSMB, Clinical Event Adjudication Committee (CEC) or Operating Committee of a competing device trial. Members will not have any affiliation with the core laboratories, the data coordinating center, or the principal investigator of the trial. The DSMB committee will review all safety data from the HOVER Trial and make recommendations based upon the safety analyses. The frequency of the DSMB meetings will be determined prior to study commencement; however, the DSMB may call a meeting at any time if there is reason to suspect safety is an issue. DSMB oversight for this trial is expected to be rigorous with frequent review of all essential safety data. The DSMB chairperson will notify the principal investigator of any safety or compliance issues. They will also provide confidential recommendations, when necessary, of study termination. All DSMB reports will remain strictly confidential, but will be made available to regulatory authorities. The principal investigator will notify the FDA if any member of the DSMB advises to terminate the study due to safety concerns.

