4.1.3. Interim Monitoring and Stopping Rules

The interim monitoring and stopping rules will focus on the 6-month mortality. Based on current literature, it is reasonable to assume a 6-month mortality of at least 30% for the high risk patients targeted in this clinical trial ³¹. For the purpose of this trial, we will focus on device-related mortality.

The interim monitoring will be implemented with stopping rules when 3, 6, and 9 patients have been enrolled and treated with the protocol device. The proposed stopping rules are:

Number of patients on trial:	When number of 6-month deaths \geq :	Probability of stopping the trial early when the true 6-month mortality is 30%:
3	2	0.216
6	3	0.105
9	4	0.064
15	6	0.064

As it can be seen from the above table, the probability of stopping the trial early is very small ($\leq 10.5\%$) assuming the true 6-month mortality rate is no more than 30% when there are at least 6 patients

enrolled and treated on the clinical trial. When there are only 3 patients enrolled, we are only stopping the trial early when two (or more) out of the first three patients died within 6 months on trial due to a device-related death. This probability is reasonably small as well (21.6%).

In addition to mortality, should valve thrombosis occur in $\geq 30\%$ of patients at 6-months, the trial will be paused to evaluate if any additional precautions are required.

The trial PI ([name] [name], MD), working along with the study DSMB, will monitor other safety parameters such as significant surgery complications, one-year mortality, overall survival, and event-free survival at least biannually (every 6 months) as well in an effort to make certain that the patients on trial are not inadvertently harmed by the proposed protocol treatment.

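### Section 4.1.3 counts a row at 15 patients as early stopping, but 15 is the full sample, so no numerical mortality boundary can act before implants 10 to 15

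*Combined protocol and SAP*

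**What the plan says.** The sample is fixed at 15. The protocol summary says "A total of 15 patients will undergo implantation", and section 2.3 says "A total of up to 15 patients will be enrolled".

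Section 4.1.3 places the looks as follows: "The interim monitoring will be implemented with stopping rules when 3, 6, and 9 patients have been enrolled and treated with the protocol device". Its table has four rows: 2 or more deaths at 3 patients, 3 or more at 6, 4 or more at 9, and 6 or more at 15. The probabilities beside them are 0.216, 0.105, 0.064 and 0.064, in a column headed "Probability of stopping the trial early when the true 6-month mortality is 30" (per cent). The deaths counted are restricted: "For the purpose of this trial, we will focus on device-related mortality".

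Section 2.3 refers back to this rule ("In particular, formal stopping rules on the 6-month mortality are stipulated in this protocol") and adds no other mortality boundary. Neither section says whether the counts apply only at the named looks or as deaths occur.

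**The concern.** The text names three looks and the table has four rows. The fourth row falls when every planned patient has been implanted, so as a look it cannot stop anything early. The rule is the only formal mortality boundary in a study of an off-label implant. A reader who adds up the table would credit it with protection that it cannot give to patients 10 to 15.

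The second gap is what happens between looks. Suppose 1 of the first 3 patients and 3 of the first 5 have a counted death. The 3-patient boundary was not met, but the 6-patient boundary is now certain to be met, because a death count cannot fall. The text does not say whether the sixth implant goes ahead.

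**Working it through.** **Inputs.** Boundaries 2/3, 3/6, 4/9 and 6/15 and true mortality p = 0.30 (section 4.1.3 table); 15 implants (protocol summary). Like the table, the check takes outcomes as independent and known at each look. The 50% scenario is mine, for illustration; the documents give only 30%.

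**Reproducing the table.** For each row, find the probability of reaching the boundary there and not at an earlier row.

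- *At 3:* 3(0.3²)(0.7) + 0.3³ = 0.2160. The trial continues with 0 deaths (0.3430) or 1 death (0.4410).
- *At 6:* 0.3430 × P(3 of 3) + 0.4410 × P(≥2 of 3) = 0.3430 × 0.027 + 0.4410 × 0.216 = 0.1045. It continues with 0, 1 or 2 deaths (0.1176, 0.3025, 0.2593).
- *At 9:* 0.3025 × 0.027 + 0.2593 × 0.216 = 0.0642. It continues with 0, 1, 2 or 3 deaths (0.0404, 0.1556, 0.2446, 0.1747).
- *At 15:* 0.0404 × P(6 of 6) + 0.1556 × P(≥5 of 6) + 0.2446 × P(≥4 of 6) + 0.1747 × P(≥3 of 6) = 0.0404 × 0.0007 + 0.1556 × 0.0109 + 0.2446 × 0.0705 + 0.1747 × 0.2557 = 0.0636.

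All four match the printed values. Simple binomial tails (0.216, 0.256, 0.270, 0.278) match only the first row, so the rows are first-crossing probabilities and can be added.

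**What can still stop an implant.** At 30%, looks 3, 6 and 9 give 0.2160 + 0.1045 + 0.0642 = 0.385. Adding row 15 gives 0.448. At 50%, the looks give 0.5000 + 0.2031 + 0.1055 = 0.809, and row 15 adds 0.0946, for a total of 0.903. The share implanted after the last named look is (15 − 9)/15 = 40%. With fixed looks, a trial that passes the 9-patient look with 3 deaths could lose all six later patients, 9 of 15, without the rule withholding an implant.

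**Applying each count as deaths occur.** Deaths only accumulate, so a boundary reached inside a block is also met at the block's end, and the four tabulated values do not change. What changes is when the stop happens. After patient 9 at most 3 deaths are on the count, so 6 deaths can be reached at patient 12 at the earliest. At 30%, the probability of passing patient 9 and reaching 6 deaths by patient 14 is

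0.1556 × P(5 of 5) + 0.2446 × P(≥4 of 5) + 0.1747 × P(≥3 of 5) = 0.1556 × 0.0024 + 0.2446 × 0.0308 + 0.1747 × 0.1631 = 0.036.

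| | 30% | 50% |
|---|---|---|
| Stop before 15th implant, fixed looks | 0.385 | 0.809 |
| Stop before 15th implant, counts applied as deaths occur | 0.421 | 0.875 |
| Total crossing, either reading | 0.448 | 0.903 |
| Expected patients treated, fixed looks | 11.08 | 6.54 |
| Expected patients treated, counts applied as deaths occur | 10.87 | 6.03 |

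For fixed looks at 30%, expected patients treated = 3(0.2160) + 6(0.1045) + 9(0.0642) + 15(1 − 0.3847) = 11.08.

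**The case against.** Four replies have force.

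*Oversight does not end at patient 9.* A reader might infer that patients 10 to 15 have no safety protection. The documents do not support that. Section 4.1.2 provides that "the DSMB may call a meeting at any time if there is reason to suspect safety is an issue", and the DSMB can recommend termination. Section 7.2 has serious adverse events reported to the DSMB chair within 24 hours of discovery. Section 4.1.3 has overall survival reviewed at least every 6 months and pauses the trial if valve thrombosis reaches 30%. Section 2.3 provides that "the patient accrual to the trial will be suspended immediately, pending a review of all adverse events data", though for other adverse events judged excessive. What stands is narrower: none of these gives a mortality threshold.

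*The rule may already be meant to act between looks.* A reader might infer that it does not. The text points to fixed looks, but both readings give the same four probabilities, so the table cannot settle it, and nothing forbids acting on a boundary already met. This is a matter to clarify, not a proven defect.

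*Waiting costs little in the early blocks.* A trial that continues has at most 1 death at 3 patients and at most 2 at 6, so the earliest crossings are at patients 2, 5 and 8, and waiting for the look costs one implant at most in each block. Three deaths among the first four patients would be a false illustration: they always include two among the first three, which already meets the first boundary.

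*At the plan's own 30% the effect is modest.* A trial that passes the 9-patient look has a 0.0636/0.6153 = 10% chance of reaching 6 deaths by patient 15, and 0.0364/0.6153 = 6% by patient 14. The larger figures, 0.0946/0.1914 = 49% and 0.0663/0.1914 = 35%, belong to the 50% scenario.

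**Conclusion.** The point stands as a mismatch between text and table with a practical consequence. As a look, the 15-patient row cannot spare an implant, so 0.064 of the 0.448 crossing probability at 30% mortality is wrongly described as early stopping. Implants 10 to 15 have no numerical mortality boundary that can act before them. Whether the rule acts between looks is unstated.

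The result assumes that all 15 patients are implanted, that outcomes are independent, and that they are known at each look. The last is favourable to the plan: looks are triggered by patients treated, while the endpoint runs to 6 months, so real stopping would come later. The 30% is applied to the counted deaths, as the table does. If device-related mortality is lower, the probabilities shrink: at 20%, looks 3, 6 and 9 total 0.172 and row 15 adds 0.017. The section should be corrected, but the feasibility design itself is not in question.

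**What to change.** Reword section 4.1.3 so that accrual stops as soon as counted deaths reach 2 within the first 3 patients, 3 within the first 6, 4 within the first 9, or 6 within the first 15, with the DSMB applying this at each counted death. Describe the last row as acting during patients 10 to 15. The text and table then agree, and the four counts and probabilities stay as printed.

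Costs: at 30% mortality the chance of halting before the last implant rises by 0.036, from 38.5% to 42.1%, and someone must judge promptly whether each death is device-related. Existing 24-hour reporting already brings deaths to the DSMB chair. Some of row 15 still cannot spare an implant, because the sixth death may be that of patient 15: 0.0636 − 0.0364 = 0.027 at 30%.

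If fixed looks are preferred, one could be added at 12 patients with at least 5 deaths, a boundary chosen here for illustration. The table must then be recalculated: at 30% the new row is 0.044, row 15 falls to 0.033 and the total rises to 0.462. The chance of stopping before the 15th implant would be 0.385 + 0.044 = 0.429 at 30%, and 0.870 at 50%.

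### Section 4.1.3 reads first-crossing probabilities row by row as a chance of at most 10.5% of stopping early from 6 patients on; at a 30% counted death rate they add to 16.9% (looks at 6 and 9) or 23.2% (adding 15)

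*Combined protocol and SAP*

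**What the plan says.** Section 4.1.3 (Interim Monitoring and Stopping Rules) sets boundaries of 2 deaths among 3 patients, 3 among 6, 4 among 9 and 6 among 15. The third column of its table is headed "Probability of stopping the trial early when the true 6-month mortality is 30" percent, with entries 0.216, 0.105, 0.064 and 0.064.

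The text below the table says "the probability of stopping the trial early is very small", gives 10.5% as the upper limit, and sets the scope as "assuming the true 6-month mortality rate is no more than 30% when there are at least 6 patients" enrolled and treated. The 21.6% at the 3-patient look is given separately and also described as reasonably small. No overall probability of stopping is stated, and neither the header nor the text says how the rows relate to one another.

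Two other statements bear on what the figure means:

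- **Which deaths count.** Section 4.1.3 says "For the purpose of this trial, we will focus on device-related mortality". The column header and the 10.5% sentence refer only to 6-month mortality, as does section 2.3, which says "formal stopping rules on the 6-month mortality are stipulated in this protocol".
- **Which looks exist.** The text describes "stopping rules when 3, 6, and 9 patients have been enrolled and treated with the protocol device". The table has a fourth row at 15, and section 2.3 says "A total of up to 15 patients will be enrolled".

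**The concern.** The sentence gives one probability of stopping early for a trial that has reached at least 6 patients. That span contains two further looks named in the text, and a third if the 15-patient row counts. If the rows are probabilities of stopping first at each look, the chance of stopping over the span is their sum, and the largest row understates it.

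Section 2.3 calls these the formal stopping rules, and this column with its commentary is the only operating characteristic the plan gives for them. The DSMB, the IRBs and the sponsor cannot tell from section 4.1.3 how often the rule would halt the trial at the rate the plan itself assumes.

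**Working it through.** **Inputs.** Boundaries and the 30% rate come from the table in section 4.1.3; maximum enrolment of 15 comes from section 2.3. The calculation treats every patient's 6-month status as known at each look. The plan's table reproduces on this basis.

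**Method.** Exact binomial recursion. Carry forward the distribution of deaths among trials that have not stopped, add the next group of patients, and remove the paths that reach the boundary. With p = 0.30, a group of 3 has 0, 1, 2 or 3 deaths with probability 0.343, 0.441, 0.189, 0.027, so P(2 or more of 3) = 0.216.

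**Reproducing the plan's column.**

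- *Look at 3 (2 or more deaths):* 0.216. Continuing: 0 deaths 0.343; 1 death 0.441.
- *Look at 6 (3 or more):* 0.343 × 0.027 + 0.441 × 0.216 = 0.00926 + 0.09526 = **0.1045**. Continuing: 0 deaths 0.1176; 1 death 0.3025; 2 deaths 0.2593.
- *Look at 9 (4 or more):* 0.3025 × 0.027 + 0.2593 × 0.216 = 0.00817 + 0.05601 = **0.0642**. Continuing: 0 deaths 0.0404; 1 death 0.1556; 2 deaths 0.2446; 3 deaths 0.1747.
- *Row at 15 (6 or more, after 6 further patients):* 0.0404 × 0.0007 + 0.1556 × 0.0109 + 0.2446 × 0.0705 + 0.1747 × 0.2557 = **0.0636**.

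All four agree with the table to three decimals. Other readings of the column do not:

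| Reading of the column | n=3 | n=6 | n=9 | n=15 |
|---|---|---|---|---|
| Plan's table | 0.216 | 0.105 | 0.064 | 0.064 |
| First crossing at this look | 0.2160 | 0.1045 | 0.0642 | 0.0636 |
| Single-look binomial tail | 0.216 | 0.256 | 0.270 | 0.278 |
| Conditional on reaching the look | 0.216 | 0.133 | 0.094 | 0.103 |

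**Adding the rows.** A trial can cross for the first time only once, so the events are disjoint.

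- Looks at 6 and 9: 0.1045 + 0.0642 = 0.1687, or 16.9%. Ratio to the stated limit: 0.1687 / 0.105 = 1.61.
- Adding the row at 15: 0.1687 + 0.0636 = 0.2323, or 23.2%. Ratio: 2.21.
- Given that the 3-patient look was passed (divide by 1 − 0.216 = 0.784): 21.5% and 29.6%.
- Cumulative from the start: 0.2160, 0.3205, 0.3847, 0.4483.

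**Range over which the stated limit holds.** Setting the sum equal to 0.105 and solving for the death rate gives 24.0% for the looks at 6 and 9, and 21.7% with the row at 15. The sentence claims the limit for any rate up to 30%.

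**Other counted death rates (assumed values).** Cumulative probability of stopping:

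| Rate | By n=9 | By n=15 |
|---|---|---|
| 10% | 0.038 | 0.039 |
| 15% | 0.092 | 0.097 |
| 20% | 0.172 | 0.188 |
| 25% | 0.271 | 0.309 |
| 30% | 0.385 | 0.448 |
| 40% | 0.617 | 0.721 |
| 50% | 0.809 | 0.903 |

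**The case against.** The strongest reply is that nothing in the table is wrong. The sentence refers the reader to the table, every row from 6 patients on is at most 10.5%, and the 21.6% is disclosed. Taken one row at a time, the statement is true. But the sentence does not speak of one look; it gives a single probability for a trial with at least 6 patients. Reading it as conditional on having got that far does not help, because the 6-patient look alone is then 0.1045 / 0.784 = 13.3%.

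A second reply is that 30% is introduced as mortality in the target population, whereas the rule counts device-related deaths, which are a subset. If the counted rate were 20%, the sums from 6 patients on would be 6.8% (6 and 9) and 8.4% (adding 15); at 10% they would be 1.0% and 1.1%. This limits the practical size of the gap and is why every figure here is conditional on the counted rate. It does not rescue the sentence, which claims its limit up to 30% and rests on a table computed at 30%.

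Three further points stand. Enrolment is complete at 15, so 16.9% and 38.5% are the better figures for stopping early. The rule stops more readily than the text suggests, so patient protection is not weakened. The plan does not say that a look waits for 6-month status, so any restated figures should carry that assumption.

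**Conclusion.** The concern holds. The table is right and its interpretation is wrong. At a counted 6-month death rate of 30%, with 6-month status known for every patient at each look, the probability of stopping from 6 patients on is 16.9% over the looks at 6 and 9 (23.2% with the row at 15), against a stated maximum of 10.5%. Over the whole trial the rule stops with probability 38.5% before full enrolment, close to two chances in five, which is hard to call very small.

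The consequence is confined to a misdescribed property of the stopping rule. Boundaries, conduct and both primary endpoint estimates are unaffected. It should be corrected because it is the only quantitative description of the formal stopping rule in the plan.

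**What to change.** In section 4.1.3:

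1. Relabel the third column: *probability of first crossing at this look if the counted 6-month death rate is 30%, with 6-month status known for all patients at the look*.
2. Add a cumulative column: 0.216, 0.321, 0.385, 0.448. Note that it is computed from unrounded values, since the printed 0.385 and 0.064 would add to 0.449.
3. Replace the 10.5% sentence, for example: *If the counted 6-month death rate is 30%, the probability of stopping is 21.6% at the 3-patient look and a further 16.9% at the 6- and 9-patient looks (38.5% by 9 patients), or 44.8% in total if the 15-patient row is included.*
4. Add the cumulative values at other counted death rates from the second table above. This matters because the rate of counted deaths may differ from 30%.
5. Reconcile the looks named in the text (3, 6 and 9) with the table's row at 15, and use one definition of a counted death in the header, the text and section 2.3.

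The cost is one relabelled column, one new column, one replaced sentence and a short table. The stated chance of stopping becomes less favourable. No boundary, patient number or procedure changes.
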